	¹⁶ MUDr. [name], Všeobecná ambulancia pre deti a dorast, [name], [contact], [contact] ¹⁷ MUDr. [name]., Všeobecná ambulancia pre deti a dorast MEDMA CARE s.r.o., [name], [contact] , [contact] ¹⁸ MUDr. [name], Všeobecná ambulancia pre deti a dorast BABY CARE s.r.o., [name]; [contact] , [contact] ¹⁹ MUDr. [name], Všeobecná ambulancia pre deti a dorast, [name], [contact] ²⁰ MUDr. [name], Všeobecná ambulancia pre deti a dorast INFANTE, s.r.o., [name], [contact]
Study Design:	Multicentre, prospective, open-label study. with a novel cosmetic product.
Number of Patients:	cca. 100 patients aged from 3 weeks enrolled by investigators in 20 centres
Primary Endpoints:	
To evaluate the clinical effect of Imunoglukan P4H® ACUTE! cream paste in selected skin dermatoses (diaper dermatitis, perioral dermatitis, neonatal pustulosis) on:
 
 • Clinical assessment of erythema using a 5-point severity scale (Clinician's Erythema Assessment - CEA) • Investigator's Global Assessment (IGA) using a 6-point scale
Secondary Endpoints:	To evaluate the tolerability of the cosmetic product Imunoglukan P4H® ACUTE! cream paste in selected skin dermatoses (diaper dermatitis, perioral dermatitis, neonatal pustulosis) using a 3-point tolerability scale.

Timeline of the biomedical research

Pre-screening of patients: march-april 2024

Date of first patient inclusion: april-may 2024

Study completion date: 31. 12. 2024

Patient follow-up duration: 2 weeks, with a total of 2 visits:

- V0 – initial visit - **day of enrolment**
- photodocumentation performed by the patient/legal representative after 7 days of application
- V1 – **control visit - after complete recovery from erythema or maximum 14 days from enrolment**

Introduction

Normalization of the skin barrier defence function can be supported by using products that promote the physiological process of keratinization and the immune functions of the skin. In patients with problematic skin, the use of alternative and complementary treatments also plays an important role, as they can be used as add-on to the standard of care treatment. A significant group among complementary medicine products includes preparations containing natural substances with a proven complex immunomodulatory effect – biologically active polysaccharides (BAP), such as beta-glucans.

Biologically active polysaccharides are glucose polymers commonly found in fungi, yeasts, bacteria, and cereals. They represent some of the most extensively studied natural immunomodulators with pluripotent biological effects (anti-infective, antiviral, immunomodulatory). Imunoglukan® is a

complex of biologically active polysaccharides with a predominant content of beta-1,3/1,6-D-glucan pleuran, obtained through a patented isolation technology from *Pleurotus ostreatus*.

In topical application, Imunoglukan® activates skin immune cells (Langerhans cells – skin macrophages) through Dectin-1 receptors on one hand, and on the other hand, it can also activate skin cells that are not part of the immune system (keratinocytes and fibroblasts).

In topical application, Imunoglukan® influences:

- function and viability of Langerhans cells
- proliferation and migration of keratinocytes
- stimulation of collagen production in fibroblasts
- tissue regeneration and remodelling
- rate of wound healing
- production of certain cytokines (e.g., IL-1, IL-8, TNF- α) and enzymes (MMP-9)
- enhancement of antioxidant effects
- slowing of cellular aging

The effectiveness and safety of Imunoglukan® for various types of skin problems have been confirmed by numerous laboratory experiments, clinical observations, and open-label studies. For instance, a multicenter open-label study conducted in ten dermatological centers in Slovakia and the Czech Republic demonstrated a positive effect on alleviating the symptoms of atopic dermatitis. At the sites of cream paste application, there was a significant reduction in the number of flare days, the intensity of disease exacerbation, and the sensation of itching. Clinical trials have also confirmed very good effects of Imunoglukan® cream paste in the treatment of leg ulcers, herpetic infections, and surgical wounds following extensive oncological procedures, as well as in healing crusts after chickenpox in pediatric patients. The skin condition of patients with seborrheic dermatitis, rosacea, or acne significantly improved after cream paste application, and even an anti-aging effect was observed.

The results of clinical studies and observations confirmed the complex immunomodulatory and regenerative effects of Imunoglukan® with no recorded adverse effects.

Study Design

It is a multicentre, prospective biomedical research conducted in outpatient healthcare facilities. In terms of the nature of the study, it is a biomedical research involving the novel cosmetic product Imunoglukan P4H® ACUTE! cream paste.

Investigators/physicians will enrol a total of 100 patients who meet the inclusion criteria.

Patients enrolled in the study will apply Imunoglukan P4H® ACUTE! cream paste at least 2–3 times daily (or as needed) in an appropriate layer to the affected area for a maximum duration of 2 weeks.

Ingredients (INCI): Aqua, Zinc Oxide, Neopentyl Glycol Dipelargonate, Cetyl PEG/PPG-10/1 Dimethicone, Triolein, Magnesium Stearate, Gluconolactone, Polyglyceryl-4 Isostearate, Glycerin, Sodium Hyaluronate, Beta-glucan, Zea Mays Starch, Tocopheryl Acetate, C10-18 Triglycerides, Glyceryl Dioleate, Polyvinyl Alcohol, Magnesium Sulfate, Sodium Benzoate, Calcium Gluconate.

The effect of the application of Imunoglukan P4H® ACUTE! cream paste on the clinical status of erythema in skin disease will be assessed by both the physician and the patient/legal representative using a 5-point severity scale (Clinician's Erythema Assessment – CEA) and through the Investigator's Global Assessment (IGA) on a 6-point scale. The tolerability of the cosmetic product Imunoglukan P4H®

ACUTE! cream paste in the selected indications will be assessed by the physician using a 3-point tolerability scale.

Discussion on the design

The multicentre, prospective design of the research provides a basis for obtaining clinically, scientifically, and statistically significant results with the aim of clarifying the impact of the investigated intervention on the primary and secondary objectives. For the clinical evaluation of erythema focused on reducing and alleviating the duration of selected skin problems, a 2-week follow-up period is justified. In addition to confirming the basic hypothesis, the pilot study should also provide data on the tolerability, safety, and potential adverse effects.

Subjects enrolled in the biomedical research will undergo anamnesis data collection during follow-up visits and will continuously complete the relevant questionnaire (Patient Diary).

Project endpoints:

Primary endpoints – to evaluate the clinical effect of the cosmetic product Imunoglukan P4H® ACUTE! cream paste in patients with selected skin dermatoses (diaper dermatitis, perioral dermatitis, neonatal pustulosis) on:

- Clinical assessment of erythema using a 5-point severity scale (Clinician's Erythema Assessment)
- Investigator's Global Assessment (IGA) using a 6-point scale

Secondary endpoints – to evaluate the tolerability of the cosmetic product Imunoglukan P4H® ACUTE! cream paste in patients with selected skin dermatoses using a 3-point tolerability scale.

Inclusion criteria

- signed informed consent
- age ≥ 3 weeks
- diagnosis (at least one of the following):
 - perioral dermatitis
 - diaper dermatitis
 - neonatal pustulosis

Non-inclusion criteria

- refusal to provide informed consent
- ongoing application of topical corticosteroids, antihistamines or other immunomodulatory products
- ongoing use of oral corticosteroids or antihistamines
- known intolerance to any components of the investigational product

Exclusion criteria

- application of topical corticosteroids, antihistamines, or other immunomodulatory products
- use of oral corticosteroids or antihistamines
- intolerance to the investigational product

Patient Instruction

The attending physician will instruct the patient/legal representative on the **elimination of irritating factors** (such as soaps, shampoos, bath foams, perfumed wet wipes, sucking on hands/fingers/toys/food, etc.) and on **refraining from using any other products** for the topical treatment of the diagnosed skin condition during the course of the study.

List of data collected from subjects enrolled in the study

Basic Identification Data	
 ○ Patient's code ○ Patient's initials ○ Date of birth ○ Date of the CRF / Visit date
Medical History and Demographic data	
 ○ Age ○ Gender ○ Current comorbidities ○ Current treatment of the comorbidities
Diagnostic Procedures	
 ○ Clinical assessment of erythema using a 5-point severity scale ○ Investigator's Global Assessment (IGA) using a 6-point scale ○ Assessment of cosmetic product tolerability using a 3-point scale
Primary Endpoints	
 ○ Evaluation of the clinical status of erythema after treatment ○ Overall severity and improvement of selected dermatoses by the investigator
Secondary Endpoints	
 ○ Evaluation of product tolerability

Visit schedule and assessment timeline

Number of the visit	V0	V1
Time of the visit	Initial examination	After the disappearance of symptoms, or after 14 days
Informed consent	X	
Inclusion/Non-inclusion criteria	X	
Exclusion criteria	X	
Demographic data	X	
Medical history	X	
Comorbidities	X	
Dispensing of medication	X	
Clinical assessment of erythema (CEA)	X	X
Investigator's Global Assessment (IGA)		X
Assessment of tolerability		X
Number of papules in selected dermatoses	X	X
Adverse events		X
Photodocumentation of the affected area	X (physician)	X (physician)

Patient diary (completed continuously by the patient/parent)	X	X
--	---	---

Required diagnostic procedures

Clinical assessment of erythema (Clinician's Erythema Assessment – CEA)

At each visit, the physician will record in the CRF the value based on the Clinical Erythema Assessment (CEA) scale using a 5-point scale:

- 0 = no erythema
- 1 = very mild erythema: light pink
- 2 = mild erythema: pink
- 3 = moderate erythema: red
- 4 = severe erythema: intense red

Investigator's Global Assessment (IGA)

At visits V0 and V1, the physician will record in the CRF the value based on the Investigator's Global Assessment (IGA) using a 6-point scale:

- -1 = worsening
- 0 = no response
- 1 = mild response: 10–30% improvement
- 2 = moderate response: 31–60% improvement
- 3 = excellent response: 61–90% improvement
- 4 = complete response: 91–100% – clear improvement

Assessment of cosmetic product tolerability

At visit V1, the physician will record in the CRF the assessment of tolerability using the following scale:

- 0 = poor
- 1 = good
- 2 = excellent

Adverse event log

In the event of adverse events, the physician will complete the log and record the occurrence of adverse events in the CRF.

Patient diary

Throughout the study, the patient/parent will record selected parameters daily to assess the progress of the skin condition.

Amendments to the Protocol, Other changes in the Conduct of Biomedical Research

Any changes to the protocol will be implemented in the form of a Protocol Amendment. Changes in the conduct of the biomedical research are not permitted.

Personal Data Protection

All patients in this project will be identified using a unique ID. Patient identification using this ID will not be possible. Source data may only be verified by the monitor. The unique ID of a particular patient will be known only to the physician or monitor. Personal identification data included in this project will consist of: date of birth, gender, and patient initials. The nature of personal data identifiers complies with all relevant legislative requirements.

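### Erythema (CEA) is a primary endpoint, but entry requires no erythema and no scored site is fixed, so some patients cannot improve on CEA and others may be rated on different sites at V0 and V1

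*Protocol*

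**What the plan says.** **Entry.** The Inclusion criteria section lists consent, age of 3 weeks or more, and a "diagnosis (at least one of the following" perioral dermatitis, diaper dermatitis or neonatal pustulosis. The non-inclusion and exclusion lists deal with consent refusal, corticosteroids, antihistamines, immunomodulatory products and intolerance. None sets a minimum severity.

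**Endpoint.** Project endpoints names two primary measures. The first is "Clinical assessment of erythema using a 5-point severity scale (Clinician's Erythema Assessment"; the second is IGA. Under Required diagnostic procedures the CEA scale runs from 0 (no redness) to 4.

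**Scoring.** The same section says: "At each visit, the physician will record in the CRF the value based on the Clinical Erythema Assessment (CEA) scale". It names no site and gives no rule for a patient with more than one affected area. Study Design has the product applied "in an appropriate layer to the affected area for a maximum duration of 2 weeks".

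**Timing of V1.** The Timeline section says "after complete recovery from erythema or maximum 14 days from enrolment". The Visit schedule table instead ties V1 to symptoms having gone, or to 14 days.

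**Other signs.** The Visit schedule includes "Number of papules in selected dermatoses" at V0 and V1. This is not a primary endpoint.

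**Data listed.** The List of data collected covers identification, age, gender, comorbidities and their treatment, and the three assessments. It shows no field for the qualifying diagnosis or the site scored.

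**The concern.** The study describes no control arm, so within-patient change from V0 to V1 carries the evidence. That change needs room to improve at V0 and the same skin rated at both visits. The Protocol secures neither for CEA.

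A patient with lesions but no redness satisfies every entry criterion. On CEA the only possible outcomes are no change or worsening. The separate papule count shows that the Protocol expects signs other than redness, so such a patient is possible on its own terms.

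A patient with two of the three dermatoses also satisfies every criterion. With no site fixed, each physician in the 20 centres decides what to rate, and may decide differently at the two visits. If the site is not recorded, no later analysis plan can restore it.

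**Working it through.** **Step 1: set the sections side by side.**

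| Element | Where | What it implies |
|---|---|---|
| Diagnosis only, one or more | Inclusion criteria | CEA 0 and multiple dermatoses both admitted |
| CEA is primary, floor 0 | Project endpoints; Required diagnostic procedures | V0 CEA of 0 is a valid score and cannot fall |
| V1 "after complete recovery from erythema" or by day 14 | Timeline | Presumes erythema at V0; met at enrolment if CEA is 0 |
| V1 once symptoms have gone, or day 14 | Visit schedule | Not met by a patient with lesions but no redness |
| Physician records one CEA reading, no site named | Required diagnostic procedures | V0 and V1 sites may differ |

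For a patient with lesions and CEA 0 the two V1 rules give different dates.

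**Step 2: effect of the CEA floor.** The Protocol gives neither the share entering at CEA 0 nor an expected change, so both are assumed. The planned N is 100, stated without a derivation; it cannot be reproduced and is not disputed here. Let f be the share with V0 CEA 0 who stay at 0, and let the others have mean drop d and standard deviation s.

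- Mean drop = (1 − f)·d
- Variance = (1 − f)·s² + f(1 − f)·d²
- Highest possible rate of a drop of at least 1 point = 1 − f

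With d = 1.5 and s = 1.0 (assumed):

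- f = 10%: mean 0.9 × 1.5 = 1.35; variance 0.9 + 0.09 × 2.25 = 1.1025, SD 1.05; standardised change 1.35/1.05 = 1.29, against 1.50 with f = 0.
- f = 20%: mean 0.8 × 1.5 = 1.20; variance 0.8 + 0.16 × 2.25 = 1.16, SD 1.08; standardised change 1.11.

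The relative loss in the mean is always f. At f = 20%, for d between 1.0 and 2.0, the standardised change falls by about 18% (1.00 to 0.82) to 33% (2.00 to 1.33).

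For the responder rate, suppose 80% of patients with erythema improve by at least 1 point (assumed):

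| f | Patients of 100 able to improve | Rate observed, 0.8 × (1 − f) |
|---|---|---|
| 0% | 100 | 80% |
| 5% | 95 | 76% |
| 10% | 90 | 72% |
| 20% | 80 | 64% |
| 30% | 70 | 56% |

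**Step 3: effect of the unfixed site.** Let site A score a₀ at V0 and a₁ at V1, and site B score b₁ at V1. If A is rated at V0 and B at V1, the recorded drop is a₀ − b₁ = (a₀ − a₁) + (a₁ − b₁). The error for site A is a₁ − b₁, the difference between two sites at V1, and it can have either sign. If 5%, 10% or 20% of patients had two dermatoses (assumed), 5, 10 or 20 of 100 would have a CEA value that cannot be assigned to one indication.

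**The case against.** The strongest objection is that the harm is assumed. No section says how often CEA is 0 at entry or how often two dermatoses coexist. The Protocol does not say which summary of CEA is primary, and an SAP that is not shown could limit a CEA analysis to patients with V0 CEA of at least 1. IGA, the other primary measure, rates overall response and can improve when CEA is 0. That a single CEA reading is taken is inferred from the singular wording; the CRF is not shown and may hold more. Physician photographs at both visits may allow a check of the site.

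Much of this stands. The size is unknown, the floor concerns CEA only, and an SAP could handle the floor afterwards, with fewer patients (90 or 80 of 100 at f of 10% or 20%). It does not remove the point. Eligibility and the scored site are fixed when the patient is seen, and photographs set no scoring rule.

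A reader might infer three stronger things, which the documents do not support:

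- *That CEA 0 entrants inflate a clearance rate.* The Protocol defines no clearance rate. On change or responder summaries the floor dilutes an effect and does not create one.
- *That every CEA 0 patient would have V1 at once.* This follows from the Timeline wording but not from the Visit schedule.
- *That the trial cannot support separate claims for each dermatosis because subgroups are small.* No separate estimate per dermatosis is promised and no case mix is given. Small subgroups would also remain imprecise with a CEA minimum and a fixed site.

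**Conclusion.** The point holds in a limited form. Followed exactly, the Protocol admits patients who cannot improve on one of its two primary measures, and lets the V0 and V1 readings of that measure come from different sites in a patient with two dermatoses. It also gives two triggers for V1 that disagree for a patient with lesions but no redness.

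The text establishes the defect; its size rests on assumption. If 10% to 20% of patients enter at CEA 0 and stay there, the mean CEA change shrinks by 10% to 20% and the CEA responder rate is capped at 90% to 80%. The site problem adds an error of unknown size and direction. For a pooled analysis, the difficulty is that the rated skin may change between visits; assignment to an indication matters only if results are read by dermatosis. IGA escapes the floor, but its site is not stated either.

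**What to change.** - Add to the inclusion criteria a V0 CEA of at least 1 at the site to be scored.
- Record the qualifying diagnosis and the scored site in the CRF at V0.
- Score CEA and the papule count on that same site at V0 and V1, or score each dermatosis separately.
- Rate IGA at V1 only, as response relative to V0 at that site. IGA is a response scale, so a baseline value has no meaning. The Visit schedule already marks it at V1 only, while Required diagnostic procedures asks for it at V0 as well.
- Reconcile the V1 triggers in the Timeline section and the Visit schedule.

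The cost is protocol wording and a few CRF fields. A few patients without redness would not be enrolled. If the most severe site is chosen as the index, some regression to the mean will enter the V0-to-V1 change. With no control arm described, that must be acknowledged when the change is interpreted.

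### On-study intolerance appears to be a ground for exclusion, while tolerability is scored only at V1 with no assessment at early stopping, so the sole secondary endpoint is open to favourable outcome-dependent exclusion

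*Protocol*

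**What the plan says.** Eligibility is set out in three lists. Under Non-inclusion criteria the protocol bars patients with "known intolerance to any components of the investigational product", along with those currently on certain topical or oral drugs. Under Exclusion criteria it repeats the same items without the qualifiers for known or ongoing; the intolerance item becomes "intolerance to the investigational product". In the Visit schedule and assessment timeline, exclusion criteria have their own row, apart from inclusion and non-inclusion, and it is ticked at V0 only.

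The single secondary endpoint, under Project endpoints, is tolerability "using a 3-point tolerability scale". On timing, the section Assessment of cosmetic product tolerability says: "At visit V1, the physician will record in the CRF the assessment of tolerability using the following scale". The grades are 0 (poor), 1 (good) and 2 (excellent). The Timeline places V1 "after complete recovery from erythema or maximum 14 days from enrolment". The schedule has two visits and no column for a patient who stops early.

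Harm is also recorded elsewhere. Under Adverse event log: "In the event of adverse events, the physician will complete the log and record the occurrence of adverse events in the CRF". Adverse events are not a listed endpoint, and their row in the schedule is ticked at V1 only.

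On size, Study Design says: "Investigators/physicians will enrol a total of 100 patients who meet the inclusion criteria".

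**The concern.** A reaction to the cream is both the event that the tolerability endpoint is meant to count and, on the natural reading of the lists, a reason to exclude the patient. If exclusion comes before V1, the protocol schedules no occasion on which that patient is scored. The patients most likely to be graded poor are then the ones most likely to be missing, and the study has no control arm that could reveal the selective loss.

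A second route works in the same direction. Use of corticosteroids or antihistamines is also an exclusion criterion, so a patient given one of them for a reaction could be removed on that ground.

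What is at stake is the tolerability result. Discussion on the design says that the study should yield data on tolerability, safety and possible adverse effects, in a population that starts at 3 weeks of age.

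**Working it through.** The protocol states no expected intolerance rate and no calculation for this endpoint, so there is no figure to reproduce. The check has two parts.

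**Reading the text**

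1. If the exclusion list acted only at entry, its intolerance item would largely repeat the non-inclusion item. Dropping the qualifiers for known and ongoing makes sense if the list covers events after enrolment.
2. The schedule ticks exclusion criteria at V0 only. The product is dispensed at V0, so a reaction to it can generally not have been seen by then.
3. Hence either the criterion acts after enrolment and the schedule does not show it, or it acts at entry and is close to redundant. The two places need reconciling in both cases.
4. The protocol does not say whether a patient excluded for intolerance still attends V1, is scored, or stays in the denominator.

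**Size of the possible bias**

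Inputs: N = 100 enrolled (Study Design). The number of intolerant patients t = 2, 5 or 10 is an assumption. The fraction f of them removed without a score is also an assumption: 0, about one half, or 1. Patients who tolerate the cream are taken not to be graded poor.

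Observed proportion graded poor = (t − r) / (100 − r), where r is the number removed (f × t, in whole patients). Intervals are exact (Clopper-Pearson) 95%. For zero events in n patients the upper limit is 1 − 0.025^(1/n); for example, 1 − 0.025^(1/95) = 3.8%.

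| Intolerant (assumed) | None removed | About half removed | All removed |
|---|---|---|---|
| 2 of 100 | 2/100 = 2.0% (0.2–7.0%) | 1/99 = 1.0% (0.0–5.5%) | 0/98 (0–3.7%) |
| 5 of 100 | 5/100 = 5.0% (1.6–11.3%) | 3/98 = 3.1% (0.6–8.7%) | 0/95 (0–3.8%) |
| 10 of 100 | 10/100 = 10.0% (4.9–17.6%) | 5/95 = 5.3% (1.7–11.9%) | 0/90 (0–4.0%) |

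In the middle column r is 1, 2 and 5.

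With complete removal, the interval excludes the assumed rate at 5% and 10% but still covers it at 2%. With about half removed, the estimate is too low but the interval covers the assumed rate in all three rows. With none removed, this source causes no bias.

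**The case against.** The strongest reply is that the protocol never says an excluded patient goes unscored, misses V1 or leaves the analysis. Read literally, the schedule makes the exclusion list an entry check that removes no treated patient. Who is counted is commonly left to a statistical analysis plan, which may exist. Intolerance is not invisible either: there is a poor grade, an adverse event log, a worsening grade on the IGA, a daily diary and photographs after 7 days. The intolerance rates are invented for illustration, and this is a secondary endpoint in an uncontrolled study that the protocol itself calls a pilot.

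Most of this stands, and it rules out several stronger conclusions that a reader might draw:

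- That the endpoint is favourable by construction. This would need a rule that excluded patients are not scored, and the protocol contains none.
- That the study cannot detect poor tolerability. The other records can show a reaction, even though none of them is the scored endpoint.
- That intolerant patients drop out of the CEA and IGA results. No text says so.
- That two favourable grades out of three force a good result. The grades are coarse and have no anchors, but a physician can still record poor.

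The reply does not remove the point. An analysis plan can define the denominator, but it cannot supply scores at stopping that the protocol never schedules. The V0-only tick does not settle the matter either; it is one side of the inconsistency.

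**Conclusion.** The concern holds as an unresolved risk of bias, not as a proven one. The exclusion list most naturally removes enrolled patients on the unfavourable outcome of the sole secondary endpoint. The schedule does not agree with that reading, and nothing is assessed when a patient stops early. Any bias would favour the product.

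Its size runs from nil, if every treated patient is scored, to complete loss of the poor grades, if none of the intolerant patients is. Complete loss would mislead clearly at assumed intolerance of 5% or 10%, and less so at 2%. These figures rest on assumed rates, on 100 enrolled patients, and on poor grades coming only from intolerant patients.

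This should be fixed. It falls short of a fatal flaw because the effect depends on a rule that the protocol leaves unstated.

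**What to change.** 1. Reconcile Exclusion criteria with the Visit schedule: state whether the intolerance item applies at entry, after enrolment or both, and make the two places agree.
2. State that intolerance arising on study does not remove a patient from the study data.
3. Require the V1 assessments (tolerability, CEA, IGA and adverse events) to be completed when the product is stopped, if that is before the planned V1.
4. Report tolerability with every patient who applied the product at least once in the denominator, and show how many had no score.

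Whether the product is stopped remains a decision for the clinicians; the change concerns only what is recorded and counted.

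The cost is wording in the protocol and CRF, plus an assessment at stopping for the patients concerned. The tolerability figures may look less favourable. The change needs to precede data collection, because scores not taken at stopping cannot be reliably recovered later.
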